7. STUDY DESIGN

7.1. Study Overview

This is a Phase 2, randomized, multicenter, double-blind, multidose, placebo-controlled study to assess the efficacy and safety of BIIB093 in inhibiting the progression of traumatic intracerebral contusions in participants aged 18 to 85 years.

Approximately 60 sites in 7 countries globally are planned. The study will randomize 160 participants.

Participants must be treated with BIIB093 within 10 hours of time of trauma/LKN and within 6 hours of hospital arrival. Dosing should be initiated within 1 hour of randomization and continue for 96 hours (4 days). For participants in the 3 mg/day dose arm, treatment will be initiated similarly to the regimen in an ongoing Phase 3 study targeting edema associated with LHI. Participants will receive a bolus IV dose of 0.13 mg (given over approximately 2 minutes), followed by 2 different infusion rates (a rapid IV infusion of 0.1644 mg/h for 6 hours followed by a slow IV infusion of 0.1134 mg/h for the remaining 90 hours). In the 5 mg/day dose arm, participants will receive a bolus IV dose of 0.21 mg (given over approximately 2 minutes), followed by 2 different infusion rates (a rapid IV infusion of 0.2722 mg/h for 6 hours followed by a slow IV infusion of 0.1871 mg/h for the remaining 90 hours). These treatment rates should be administered within the limitation of the device at the site. The treatment duration will be for 96 hours for both treatment groups.

The primary endpoint of this study will be the change in total contusion volume (hematoma plus perihematomal edema) as measured by brain imaging from baseline to 96 hours, or prior to DC, IPH evacuation, or CMO, if these procedures occur before 96 hours.

[figure not shown]
Participants will also have the functional assessments (i.e., GOS-E, [REDACTED], and mRS) performed at both Day 90 and Day 180 post trauma.

After the last participant completes their Day 4 (Hour 96) Visit, data for the primary endpoint and available data for the secondary endpoints will be locked for analysis. The final database lock will occur after the last participant completes their Day 180 Follow-up Visit, marking the end of the study.

See Figure 1 for a schematic of the study design.

CONFIDENTIAL

The information contained herein may not be used, disclosed, or published without the written consent of Biogen MA Inc.

Figure 1: Study Design

h = hours; MRI = magnetic resonance imaging; NCCT = noncontrast computed tomography; SOC = standard of care; TT/LKN = time of trauma/last known normal.

Dosing must be started within 10 hours from time of trauma/last known normal and within 6 hours of hospital arrival. Dosing should be initiated within 1 hour of randomization and continue for 96 hours (4 days).

7.2. Study Duration for Participants

The total duration of study participation for each participant will be approximately 180 days; this consists of a concurrent screening and enrollment period, a treatment period of 96 hours, and a follow-up period up to Day 180.

The primary endpoint for the study is at Hour 96. All randomized participants will be followed for 180 days unless consent is withdrawn.

The end of study for a participant is considered the final study assessment at Day 180 or the Early Termination (ET) Visit.

7.3. Responsibilities of Site Staff

The attending clinician has ultimate responsibility and discretion for treating participants. The clinician will use his/her best judgment in treating participants based upon the specific clinical situation and in accordance with Good Clinical Practice (GCP).

CONFIDENTIAL

The information contained herein may not be used, disclosed, or published without the written consent of Biogen MA Inc.

7.4. Study Stopping Rules

Biogen may terminate this study at any time after informing Investigators. Investigators will be notified by Biogen or designee if the study is placed on hold, completed, or closed. An external independent data monitoring committee (IDMC) will be formed and will review safety data regularly. The study may be terminated by the Sponsor at the recommendation of the IDMC, based exclusively on safety data. Details of the IDMC responsibilities will be provided in the IDMC charter.

7.5. End of Study

The end of the study is when the last participant completes the Day 180 Follow-up Visit or ET Visit.

CONFIDENTIAL

The information contained herein may not be used, disclosed, or published without the written consent of
Biogen MA Inc.

8. SELECTION OF PARTICIPANTS

8.1. Inclusion Criteria

To be eligible to participate in this study, candidates must meet the following eligibility criteria at Screening, or at the timepoint specified in the individual eligibility criterion listed:

1. Ability to understand the purpose and risks of the study and provide signed and dated informed consent and authorization to use confidential health information in accordance with national and local subject privacy regulations *or* consent provided by an independent physician where local regulations allow, and/or provision of informed consent by the participant's legally authorized representative (LAR) in accordance with all local and national regulations *or* according to the local ethics committee's guidelines *or* by another process compliant with applicable national laws and regulations and ethics committee requirements.
2. Aged 18 to 85 years old, inclusive, at the time of informed consent.

Note: age 18 years at the time of informed consent or participant meets the minimum age of consent in accordance with national regulations (whichever is higher).

Note: for countries where the minimum age of consent is over 18 years, participants may be enrolled provided a LAR is available, and if capable, the participant assents to treatment. The LAR must consider the participant's involvement in the study and provide informed consent for the participant.

3. A score of 5 to 15 on the GCS. Assessment should be made prior to medical intervention, where possible.

Note: an enrollment cap on participants presenting with GCS 15 will be placed at 10% of total number of participants.

4. A clinical diagnosis of brain contusion with lesions within the supratentorial brain parenchyma totaling > 3 mL in volume on noncontrast computed tomography (NCCT) scan (allowing for multiple contusions) at Screening.

Notes:

- a. Participants with multifocal contusions totaling > 3 mL in volume will be included. The sum total of contusion volumes should be calculated based on the baseline imaging.
- b. Contusion volume for a single contusion (hyperintense hematoma and hypointense edema on NCCT) must be determined and documented by the Investigator or his/her designee using study-specific methods detailed in the Imaging Manual.
- c. If more than 1 NCCT scan is performed prior to randomization, eligibility should be based on the most recent NCCT scan.

CONFIDENTIAL

The information contained herein may not be used, disclosed, or published without the written consent of Biogen MA Inc.

- d. In participants meeting all inclusion/exclusion criteria except for contusion volume totaling > 3 mL, a single repeat study-specific NCCT scan may be obtained to reassess contusion volume, if feasible, within the protocol-specified time window.
5. Mechanism of injury is defined.

Note: emergency medical technicians, emergency physicians, or members of the study team can identify a likely or possible mechanism of head injury based on the clinical history and/or patient presentation.

6. Study drug (BIIB093) must be infused no more than 10 hours post trauma if known, or LKN (if time of trauma is unknown), and within 6 hours of hospital arrival. Dosing should be initiated within 1 hour of randomization and continue for 96 hours (4 days).
7. Functionally independent, in the opinion of the Investigator, prior to index head injury.
8. All women of childbearing potential and all men must practice highly effective contraception during the study and for 3 months after their last day of completing study treatment infusion.

8.2. Exclusion Criteria

Candidates will be excluded from study entry if any of the following exclusion criteria exist at Screening, or at the timepoint specified in the individual criterion listed:

1. In the judgment of the Investigator, patient is likely to have supportive care withdrawn within 24 hours.
2. Indication for immediate evacuation of IPH or DC.
3. Clinical signs of brainstem herniation, in the opinion of the Investigator.
4. NCCT or MRI evidence of penetrating brain injury impacting the brain parenchyma. Cerebrospinal fluid leak in isolation is not exclusionary unless evidence of parenchymal penetration by an external force (e.g., blunt object, bullet, or depressed skull fracture).
5. Any presence of midbrain or posterior fossa injury as assessed by imaging and clinical examination.
6. Symptoms and imaging suggestive of diffuse axonal injury as the predominant injury, in the opinion of the Investigator.
7. Intracranial hemorrhage due to causes other than TBI (e.g., spontaneous intracerebral hemorrhage, saccular/fusiform/infective aneurysm rupture), based on medical history of no trauma and location of the bleed.

CONFIDENTIAL

The information contained herein may not be used, disclosed, or published without the written consent of Biogen MA Inc.

8. Coagulopathy (international normalized ratio [INR] > 1.5, activated partial thromboplastin time [PTT] > 60 s, or fibrinogen < 1.0 g/L), severe anemia (hemoglobin < 85 g/L), or thrombocytopenia (platelets < 75,000 cells/mm³) at Screening.
9. Symptoms, in the opinion of the Investigator, or electrocardiogram (ECG)-based signs (QT interval corrected for heart rate [QTc] > 520 ms) of myocardial ischemia or unstable angina at Screening, based on local assessment.
10. ECG evidence of second- or third-degree heart block or cardiac arrhythmia associated with hemodynamic instability.
11. Presence of concomitant spinal cord injury as assessed by imaging and clinical examination.
12. Injury to ascending aorta, carotid, or vertebral arteries.
13. Severe or unstable concomitant condition or disease (e.g., known significant neurologic deficit, cancer, sepsis, hematologic or coronary disease) that in the opinion of the Investigator may increase the risk of study participation or uninterpretable results, if known.
14. Patients with, in the opinion of the Investigator, life expectancy < 3 months not related to current brain contusion, or those unlikely to be compliant with follow-up.
15. Patients in whom a peripheral IV line cannot be placed.
16. Mentally incompetent (prior to trauma) patients and wards of the state, if known.

Medical History

17. Known allergy to BIIB093 or another sulfonylurea drug or any of the components of the formulated BIIB093 or matching placebo.
18. Participants who are known to have taken oral glibenclamide within the past 10 hours.
19. A clinically significant severe form of renal or hepatic disorder in the Investigator's opinion from the patient's history (e.g., dialysis), if known.
20. Known history of G6PD deficiency.
21. Clinically significant hypoglycemia in the Investigator's opinion based on known medical history or screening laboratory assessments (i.e., screening BG < 70 mg/dL [~3.9 mmol/L]).
22. Patients who have or have ever had diabetic ketoacidosis or diabetic coma/precoma, if known.

CONFIDENTIAL

The information contained herein may not be used, disclosed, or published without the written consent of Biogen MA Inc.

23. Uncontrolled hypertension (defined as systolic blood pressure > 200 mmHg continuously for over 60 minutes).
24. Hemodynamic instability (use of inotrope or vasopressor therapy or resuscitation requiring > 6 L crystalloid or colloid).

Note: transient vasopressor used to support blood pressure during specific procedures (e.g., intubation or hypotension associated with sedation/analgesics) is permitted.
25. Diabetes controlled with sulfonylurea medication, if known.
26. Life-threatening or nonsurvivable polytrauma, per Investigator's judgment.
27. Cardiopulmonary resuscitation required at any point after injury or suspected anoxic brain injury based on clinical judgment.
28. History, within the past 6 months, of decompensated congestive heart failure (New York Heart Association heart failure Class III or IV – Class III: marked limitation in activity due to symptoms, even during less-than-ordinary activity, e.g., walking short distances [20 to 100 m]; class IV: severe limitations, experiences symptoms even while at rest. Mostly bedbound patients), if known.
29. Acute Coronary Syndrome within 3 months, if known.
30. Likely to be moved to CMO in the next 24 to 96 hours, in the opinion of the Investigator.

Medications

Every effort should be made to determine if patient was taking any of the following medications prior to randomization:

31. Use of potent organic anion transporting polypeptide (OATP) inhibitors (e.g., IV rifampin, cyclosporine) within 5 half-lives of the drug prior to enrollment, if known.
32. Use of novel oral anticoagulants [NOAC] (including direct thrombin inhibitors such as dabigatran, or Factor Xa inhibitors such as rivaroxaban or apixaban), in preceding 3 days prior to the injury, if known.

Note: Patients in whom NOAC anticoagulation can be adequately reversed with Andexanet alfa may be enrolled after the Andexanet alfa infusion has been completed. This applies to the NOACs apixaban or rivaroxaban.

33. Use of antiplatelet therapy other than acetylsalicylic acid in the preceding 7 days prior to the injury, if known.
34. Use of vitamin K antagonists within 5 days prior to the injury, if known.

CONFIDENTIAL

The information contained herein may not be used, disclosed, or published without the written consent of Biogen MA Inc.

Note: patients on vitamin K antagonists who are subtherapeutic with INR < 1.5 may be included. If a patient can be adequately reversed from vitamin K antagonism to a subtherapeutic INR in time for randomization, this is acceptable, and the patient should be screened for enrollment.

Other

35. Females who are pregnant or women of childbearing potential with a positive urine or serum pregnancy test at the time of admission.
36. Nursing women who are unable to stop breastfeeding during study treatment infusion and for 7 days following the end of study treatment infusion.
37. Known current participation or known history of participation in any other investigational study that involved treatment with an investigational drug or device within 30 days prior to enrollment and for the duration of the current study participation.
38. Inability to comply with study requirements.
39. Other unspecified reasons that, in the opinion of the Investigator, make the participant unsuitable for enrollment.

CONFIDENTIAL

The information contained herein may not be used, disclosed, or published without the written consent of
Biogen MA Inc.

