16.2.2. Methods of Analysis

16.2.2.1. General Considerations

Summary statistics will be presented by treatment group. By-treatment-group analysis will be displayed as placebo, BIIB093 3 mg/day, BIIB093 5 mg/day, BIIB093 combined, and total (if applicable). For continuous endpoints, summary statistics will generally include the number of participants with data, mean, SD, median, quartiles, and range. For categorical endpoints, frequency and percentage of participants in each category will be presented. Statistical testing for efficacy endpoints will be performed between the BIIB093 (3 mg/day or 5 mg/day) and placebo groups. All tests will be 2-sided with a significance level equal to 0.05 (unless otherwise specified).

CONFIDENTIAL

The information contained herein may not be used, disclosed, or published without the written consent of Biogen MA Inc.

Multiplicity will not be adjusted for the tests of the primary and secondary endpoints.

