16.8. Sample Size Considerations

The study is planned to randomize approximately 160 participants. The primary endpoint for the study is the change in total contusion volume (hematoma plus perihematomal edema) as measured by brain imaging from baseline to 96 hours, or prior to DC, IPH evacuation, or CMO, if these procedures occur before 96 hours. Assuming the common standard deviation of 29 mL in contusion volume change from baseline, a sample size of 160 participants (40 each in the 3 mg/day dose or matching placebo arms and 40 each in the 5 mg/day dose or matching placebo arms) will have approximately 90% power to detect assumed average difference of 15 mL between the pooled active treatment groups (n=80) and pooled placebo groups (n=80) using 2 group t-test at a 2-sided significance level of 5%.

CONFIDENTIAL

The information contained herein may not be used, disclosed, or published without the written consent of Biogen MA Inc.

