26. Life-threatening or nonsurvivable polytrauma per Investigator's judgement. (intra-abdominal or orthopedic trauma) requiring operative surgical management, if known. Minor fractures requiring splinting or reduction of dislocations are permitted, as are non-operative intra-abdominal injuries or placement of noninvasive external fixation devices.

Note: as per the Investigator's discretion, radiology procedures for embolization are allowed, provided they are minor and not associated with large volume bleeding.

Rationale: Exclusion criterion 26 was reworded to specify life-threatening or nonsurvivable polytrauma, based on site feedback that many patients with contusions have polytrauma. Patients with non-life threatening/survivable polytrauma may benefit from the drug, and enrollment of these patients would increase generalizability of results. Polytrauma that is normally survivable will have minimal impact to the primary endpoint of change in total contusion volume (hematoma plus perihematomal edema) for the following reasons:

- a. Polytraumas that lead to significant hematologic derangements will be excluded through laboratory exclusion criteria. Hematologic derangements would likely affect hematoma expansion.

CONFIDENTIAL

The information contained herein may not be used, disclosed, or published without the written consent of Biogen MA Inc.

- b. Polytraumas that are likely nonsurvivable would likely lead to significant volume of fluid to resuscitate the patient which would likely lead to some effect on our primary outcome.
- c. Current TBI outcome predictors (IMPACT, CRASH) do not utilize the degree of polytrauma in their functional outcomes.

Section 16.7, Interim Analysis

Change: An interim analysis was added to the protocol.

Now reads:

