### **5.3.2. Baseline Disease Characteristics per CRFs**

- Time (hours) to randomization post injury or LKN
- Time (hours) to initiation of study drug infusion post injury or LKN
- Time (hours) to NCCT for eligibility post injury or LKN
- Time (hours) to initiation of study drug infusion from NCCT for eligibility
- Injury types
- Baseline GCS before randomization
- Total injury severity scoring (ISS) score excluding head or face
- Baseline brain contusion volume (mL) per investigator
- Baseline brain contusion volume (mL) per the central review
- Baseline hematoma volume (mL) per the central review
- Baseline edema volume (mL) per the central review
- Baseline blood glucose
- Baseline alcohol level
- Baseline sodium

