### 5.6.1. General Analysis Methods for Efficacy Endpoints

All endpoint models (binary logistic regression, ordinal logistic regression, Cox model, and analysis of covariance) below will regress the outcome on the randomized treatment group, comparing the BIIB093 combined with placebo groups, adjusting for all the IRT stratification factors at randomization (see [Section 3.5.1](#)), baseline contusion volume per the central review and baseline GCS.

Analysis of covariance (ANCOVA) will be performed to compare the change in total contusion volume (primary analysis), change in absolute hematoma volume, the change in absolute edema volume, [REDACTED] from baseline in the main analysis comparing the BIIB093 combined with placebo groups. The least square (LS) mean difference with the corresponding 2-sided 95% CI and p-values for the treatment group will be provided.

Binary logistic regression will be used for binary outcomes comparing the BIIB093 combined with placebo groups. Odds ratio, the corresponding 2-sided 95% confidence interval (CI) and p-value will be reported for the treatment group.

Ordinal logistic regression (proportional odds model) will be used for GOS-E as a 7-category ordinal scale (1/2, 3, 4, 5, 6, 7, 8) and for mRS as a 5-category ordinal scale (0/1, 2, 3, 4, 5/6) at Day 90 and 180. Odds ratio, the corresponding 2-sided 95% CI and p-value for the treatment group will be reported.

The proportional odds ratio assumption will be tested using likelihood ratio test based on observed data. In the case the assumption does not hold (p-value < 0.05) or non-convergence, the Mann-Whitney test will be used as the primary inference and the source of non-proportionality or non-convergence will be investigated. Following the Mann-Whitney test, dichotomized analysis will be conducted to assess the treatment effects.

The Cox proportional hazard model will be used to assess the treatment effect on overall survival at Day 90 for all randomized participants. Hazard ratio, 2-sided 95% CI as well as the p-value for the treatment group will be reported. Kaplan-Meier curves will be presented by randomized treatment group, and Greenwood's formula will be used to calculate the standard error of the Kaplan-Meier estimates.

Multiplicity will be not be adjusted for the tests of the primary and secondary endpoints, since the current study sample size is not powered for a moderate treatment effect on GOS-E.

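### Version 3 dropped the numeric limit on extracranial injury, yet the GOS-E, mRS and survival models leave out the extracranial ISS that the SAP lists as recorded on the CRF

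*Protocol*

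**What the plan says.** Protocol 8.2, criterion 26, excludes "Life-threatening or nonsurvivable polytrauma" as judged by the Investigator. The Version 3 amendment summary records that a separate exclusion, for an Injury Severity Score above 12 with head and face left out, was deleted so that polytrauma patients could enter. Its rationale for criterion 26 is that "Polytrauma that is normally survivable will have minimal impact to the primary endpoint of change in total contusion volume". It adds that two established TBI outcome predictors do not use the degree of polytrauma.

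The SAP postdates that amendment (Version 1.0 March 2023 and Version 2.0 July 2023, against protocol Version 3 of November 2022). SAP 5.3.2 lists "Total injury severity scoring (ISS) score excluding head or face" among the CRF baseline characteristics, to be summarized by randomized group. SAP 5.6.1 has every endpoint model "adjusting for all the IRT stratification factors at randomization" (contusion volume, GCS, age group, region), plus centrally read baseline contusion volume and baseline GCS. Protocol 16.2.2.3 gives the same set for GOS-E, mRS and survival. ISS is not in these lists, nor in the visible subgroup list of SAP 3.5.2.

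**The concern.** The amendment argues mainly from the volume endpoint. GOS-E at Day 180, mRS at Day 90 and all-cause death are different kinds of outcome. All-cause death includes death from extracranial injury by definition, and disability scales may also pick up its effects. The amendment therefore allows more variation in a baseline factor that could matter for these endpoints, while the plan records that factor and uses it only descriptively.

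Leaving a prognostic baseline variable out of an ordinal logistic or Cox model moves the estimated treatment effect toward the null and lowers power. The Version 3 rationale describes Day 180 GOS-E as the registrational endpoint in TBI studies. SAP 5.6.1 concedes that the sample size does not give adequate power for a moderate GOS-E effect, so any precision that can be recovered cheaply is worth having.

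**Working it through.** **The plan's own figure.** Protocol 16.8 claims "approximately 90% power to detect assumed average difference of 15 mL", with 80 participants per pooled group, SD 29 mL and a two-sided 5% test. The standard error is 29 × √(2/80) = 4.585 mL, and 15/4.585 = 3.271. Normal-approximation power is Φ(3.271 − 1.960) = 0.905, and the noncentral t with 158 df gives 0.902. The stated 90% reproduces. It concerns contusion volume, and this point does not touch it. No power is stated for GOS-E, mRS or survival.

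**GOS-E power with and without ISS.** The documents give no GOS-E distribution, no treatment odds ratio and no ISS effect, so all three are assumed. Two simulations of a 7-category proportional-odds outcome were run with 80 vs 80:

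- Treatment OR 1.5 and 2.0: control probabilities .20/.12/.10/.12/.14/.16/.16, a normal covariate, 600 replicates, Wald test. The Monte Carlo SE of each power figure is at most about 2 points, and the two models were fitted to the same data sets.
- Treatment OR 2.2: control probabilities .20/.12/.10/.14/.14/.15/.15, a skewed covariate, 400 replicates, likelihood ratio test. Effects of 0.3, 0.5 and 0.7 in log-odds per SD correspond to ORs of 1.35, 1.65 and 2.0.

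The ISS effect stands for what remains after GCS, age and contusion volume.

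| ISS effect, OR per SD | Treatment OR | Power without ISS | Power with ISS | Difference (points) |
|---|---|---|---|---|
| 1.0 | 1.5 | 32.5% | 32.7% | +0.2 |
| 1.0 | 2.0 | 71.5% | 71.5% | 0 |
| 1.0 | 2.2 | 83% | 83% | 0 |
| 1.25 | 1.5 | 32.8% | 32.3% | −0.5 |
| 1.25 | 2.0 | 69.7% | 70.0% | +0.3 |
| 1.35 | 2.2 | 82% | 83% | +1 |
| 1.5 | 1.5 | 26.7% | 28.7% | +2.0 |
| 1.5 | 2.0 | 64.5% | 67.3% | +2.8 |
| 1.65 | 2.2 | 76% | 80% | +4 |
| 2.0 | 1.5 | 26.5% | 31.5% | +5.0 |
| 2.0 | 2.0 | 63.7% | 69.5% | +5.8 |
| 2.0 | 2.2 | 72% | 79% | +7 |
| 3.0 | 1.5 | 24.8% | 33.2% | +8.4 |
| 3.0 | 2.0 | 54.3% | 68.7% | +14.4 |

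The −0.5 is simulation noise. The 3.0 rows show an extreme case.

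**Check by formula.** On the latent logistic scale the residual variance is 3.29, so omitting a covariate with log-odds g per SD inflates it by (3.29 + g²)/3.29. This gives 1.03, 1.08 and 1.15 at g = 0.3, 0.5 and 0.7, equivalent to a sample-size loss of about 3%, 8% and 15%.

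**Attenuation.** With a conditional treatment OR of 2.0, the average estimate without ISS was 1.91 at an ISS OR of 2.0 and 1.79 at 3.0. With ISS it was 2.03 and 2.05.

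**Chance imbalance.** The standardized ISS difference between groups of 80 has SD √(2/80) = 0.158, so P(|d| > 0.2) = 0.21 and P(|d| > 0.3) = 0.06. A 2-SE imbalance multiplies the OR by exp(2 × g × 0.158), which is 1.10 at g = 0.3 and 1.25 at g = 0.7. With no treatment effect, the model without ISS rejected in 3.5% to 5.7% of replicates, consistent with 5%.

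Power was not simulated for mRS or survival. The documents give no event rate for survival.

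**The case against.** The strongest reply is that a power loss exists only if ISS predicts outcome after GCS, age group, region and contusion volume, all of which are already in the models. The documents give no such association, and their one remark on function, about the TBI predictors, leans the other way. That stands: the effect is conditional, and a gain of 5 points needs an assumed OR of about 2.0 per SD. What remains is that absence from two prognostic models does not show absence of association in a population just opened to polytrauma, and that the cost of adjusting is close to nil if there is none.

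A reader might infer that Version 3 leaves extracranial injury without any limit. It does not. Criterion 26 is itself a limit, and other exclusions in Protocol 8.2 cover clotting and hemoglobin abnormalities, spinal cord injury, major arterial injury, short life expectancy, hemodynamic instability and resuscitation. Only the numeric threshold is gone. Participants enrolled before Version 3 entered under the cap, and the share who can exceed 12 is not given.

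A reader might also infer that chance imbalance in ISS biases the comparison. Under randomization it is random error, the test keeps its level, and the baseline table would show it. Part of the attenuation toward the null is the ordinary difference between marginal and conditional odds ratios.

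Finally, Protocol 13.1 does not confine GOS-E or mRS to disability from the head injury, but silence there proves little: the detailed rating instructions are in separate documents. Collection of ISS is also uncertain. The schedule of activities does not name it, and its eligibility role has ended.

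**Conclusion.** The point holds as an inexpensive efficiency improvement for secondary endpoints. Version 3 removed the numeric limit, the SAP lists extracranial ISS, and the GOS-E, mRS and survival models do not use it. On the assumptions above, omission costs the GOS-E analysis about 0 to 1 point of power at an ISS OR of 1.25 to 1.35 per SD, 2 to 4 points at 1.5 to 1.65, and 5 to 7 points at 2.0. There is no measurable penalty for adjusting if ISS is not prognostic.

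The documents do not support the flat statement that these analyses lose power, because the prognostic strength of ISS is assumed. They do not support a claim of bias or of type I error inflation either. The primary endpoint and its 90% power are unaffected. The gain also depends on the ordinal model being kept: SAP 5.6.1 switches to a Mann-Whitney test if proportional odds is rejected or the model does not converge, and that test carries no covariates.

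**What to change.** Before unblinding, and by staff without access to interim results (the interim analysis in SAP 4.1 includes GOS-E):

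- In SAP 5.6.1, add continuous baseline ISS excluding head or face to the covariates for GOS-E and mRS. Carry it into the GOS-E imputation model in SAP 5.1.4, so that the imputation and analysis models match.
- For time to death, add it as a prespecified sensitivity analysis. The number of deaths may be small, and the Cox model already carries several covariates.
- Confirm that ISS is still collected for all participants, and state that the SAP 5.1 rule applies: a covariate with more than 10% missing is dropped.
- Optionally add ISS (≤ 12 / > 12, the former threshold) to SAP 3.5.2. Under SAP 5.1 a subgroup smaller than about 10% of mITT participants may not be analyzed.

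The cost is SAP wording, one degree of freedom per model, and a rule for handling any missing ISS.
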